### **5.2.2.1 Replacement of Subjects in DLT Period**

In order to fully evaluate the safety of the combination therapy in this study, all subjects enrolled must meet the criteria for evaluability for Cycle 1. Subjects are considered non-evaluable and will be replaced if:

- They are enrolled but not treated,
- They discontinue from the trial prior to completing all safety evaluations due to reasons other than drug-related AEs,
- They received <90% of the total pembrolizumab infusion in Cycle 1 (e.g., because the infusion had to be discontinued due to an infusion reaction) and did not experience a drug-related event,
- They received  $\leq 75\%$  of preladenant doses intended for the trial during Cycle 1 and did not experience a drug-related AE,
- They must take a prohibited concomitant medication during Cycle 1, unless this medication is used to treat a study drug-related AE,
- They must undergo medical / surgical procedures or have logistical issues not related to study therapy (e.g., elective surgery, unrelated medical events) during Cycle 1.

Non-evaluable subjects will not be counted toward the cohort total for DLT evaluation.

Subjects who experience a DLT in Cycle 1 should be discontinued from treatment. However, if in the opinion of the Investigator, the subject is deriving clinical benefit from the study treatment, the subject may be allowed to continue on the study upon resolution of the DLT to a  $\leq$  Grade 1 adverse event and after discussion with the sponsor.

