Adverse events reported by  $\geq 5\%$  of the healthy volunteers in Phase 1 multiple-dose trials include (preladenant vs. placebo): insomnia (24% vs. 3%), headache (15% vs. 3%), dizziness (9% vs. 5%), nausea (9% vs. 1%), abdominal pain (6% vs. 3%), and energy increased (6% vs. 0%). The most common AEs reported in subjects with Parkinson's disease who received preladenant in the double-blind Phase 2 dose-finding trial P04501 were Parkinson's disease (11%), somnolence (9%), dyskinesia (7%), nausea (7%), constipation (7%), headache (7%), and dizziness (6%). Adverse events reported by subjects with Parkinson's disease in Phase 1 trials (n=52) were generally similar to AEs reported in Phase 2 trials.

In later phases of the preladenant clinical program, the following AEs have been noted as risks for preladenant: increases in liver function enzymes and transient increases in blood pressure (BP).

Two Phase 2 trials (P02541 and P03376) were terminated early by the sponsor because of asymptomatic elevated liver enzymes in P02541. In P02541, 3 of 29 subjects had liver function test (LFT) elevations that reached protocol-specified criteria for discontinuation (alanine aminotransferase [ALT]  $> 3 \times$  upper limit of normal [ULN]). Overall, in 7 of the 8 Phase 2 studies (the 8th being accounted below with the Phase 3 studies), the number of subjects / frequency of ALT or AST elevations  $\geq 3 \times$  ULN was 7/429 (1.6%) for all doses of preladenant vs 4/145 (2.8%) in the placebo group. These increases were higher in the 25, 50 and 100 mg daily dose than that in the lower dose groups (see preladenant IB).

In the unblinded Phase 2 (P6402) and four Phase 3 trials (P06402, P04938, P07037, P06153, P05664) there were a total of 52 subjects (37 on preladenant at doses ) meeting the protocol threshold for adjudication of  $\geq 3 \times$  ULN, out of 2699 treated, for an incidence rate of

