### **5.2.2 Definition of Dose-Limiting Toxicities**

All toxicities will be graded using NCI CTCAE Version 4.0 based on Investigator assessment (Appendix 12.5).

The DLT window of observation will be during Cycle 1 (Day 1 to Day 21).

The occurrence of any of the following toxicities during Cycle 1 will be considered a DLT, if assessed by the Investigator to be possibly, probably or definitely related to study drug administration:

- 1) Grade 4 non-hematologic toxicity (not laboratory).
- 2) Grade 4 hematologic toxicity lasting  $\geq 7$  days, except thrombocytopenia
  - a) Grade 4 thrombocytopenia of any duration
  - b) Grade 3 thrombocytopenia associated with bleeding
- 3) Grade 3 non-hematologic toxicity (not laboratory) lasting  $>3$  days despite optimal supportive care.

- 4) Any Grade 3 or Grade 4 non-hematologic laboratory value if:
  - Medical intervention is required to treat the subject, or
  - The abnormality leads to hospitalization, or
  - The abnormality persists for >72 hours.
  - Exceptions:
    - Clinically non-significant, treatable, or reversible laboratory abnormalities including uric acid, etc.
- 5) Any of the following liver test abnormalities are observed (Hy's Law)
  - ALT or AST > 3X ULN **with** TBL > 2X ULN with no elevation in alkaline phosphatase (AP < 2X ULN)
  - No other reasons can be found to explain the combination of increased AT and TBL, such as viral hepatitis, A,B or C, preexisting or acute liver diseases, or another drug capable of causing the observed injury
- 6) Febrile neutropenia Grade 3 or Grade 4:
  - Grade 3 is defined as ANC <1000/mm^3 with a single temperature of >38.3 degrees C (101 degrees F) or a sustained temperature of ≥38 degrees C (100.4 degrees F) for more than one hour
  - Grade 4 is defined as ANC <1000/mm^3 with a single temperature of >38.3 degrees C (101 degrees F) or a sustained temperature of ≥38 degrees C (100.4 degrees F) for more than one hour, with life-threatening consequences and urgent intervention indicated.
- 7) Prolonged delay (>2 weeks) in initiating cycle 2 due to treatment-related toxicity.
- 8) Any treatment-related toxicity which causes the subject to discontinue treatment during Cycle 1.
- 9) Missing >25% of Preladenant doses as a result of drug-related AE(s) during the first cycle.
- 10) Grade 5 toxicity.

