### **5.9 Subject Replacement Strategy**

In order to adequately evaluate the safety of the doses administered in this study, all subjects enrolled must meet the criteria for evaluability for Cycle 1. Subjects are considered non-evaluable and will be replaced if:

- They are allocated but not treated
- They discontinue from the trial prior to completing all the safety evaluations for reasons other than treatment-related adverse events
- They receive less than 90% of the total pembrolizumab infusion in Cycle 1 (e.g., if the infusion had to be discontinued due to an infusion reaction) and did not experience a DLT

Subjects who are not evaluable will be replaced unless accrual to the cohort has stopped. Non-evaluable subjects will not be counted toward the total number of subjects in the cohort for DLT evaluation.

If a subject experiences a DLT in Cycle 1, trial treatment may be discontinued following discussion between the sponsor and Investigator. However, if the subject is deriving clinical benefit from the trial treatment, the subject may be allowed to continue after discussion between the sponsor and the Investigator.

A subject who discontinues from trial treatment or withdraws from the trial during or after Cycle 2 (See Section 5.2.2.1 for subject replacement during Cycle 1) will not be replaced.

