## 8.5 Analysis Populations

### 8.5.1 Safety Analysis Population

The All-Subjects-as-Treated (ASaT) population will be used for the analysis of safety data in this study. The ASaT population consists of all subjects who received at least one dose of study treatment. In case of treatment administration errors, subjects will be analyzed according to the treatment they actually received. For DLT evaluation, ASaT subjects that were observed for safety for 21 days after the first dose of assigned treatment or experienced a DLT prior to 21 days after the first dose of assigned treatment will be used. The replacement subjects will also be considered evaluable if the above specified criteria are met.

At least one laboratory or vital sign measurement obtained subsequent to at least 1 dose of study treatment is required for inclusion in the analysis of each specific parameter. To assess change from baseline, a baseline measurement is also required. Safety data from subjects who experienced disease progression in the monotherapy arm and crossed over into the combination arm will be presented separately.

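### A subject who misses over a quarter of Cycle 1 preladenant for reasons other than toxicity, but has any minor drug-related AE, is neither a DLT nor replaced and counts as DLT-free

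*Combined protocol and SAP*

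**What the plan says.** Criterion 9 in Section 5.2.2 makes this a DLT: "Missing >25% of Preladenant doses as a result of drug-related AE(s) during the first cycle". It requires a causal link between the AE and the missed doses.

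Section 5.2.2.1 makes a subject non-evaluable, and so replaced, on receiving 75% or less "of preladenant doses intended for the trial during Cycle 1 and did not experience a drug-related AE". This condition names no grade and requires no link between the AE and the missed doses. The consequence is stated there: "Non-evaluable subjects will not be counted toward the cohort total for DLT evaluation". A separate bullet in the same list, with no AE condition, covers subjects who "have logistical issues not related to study therapy (e.g., elective surgery, unrelated medical events) during Cycle 1". Another bullet covers prohibited medication.

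Two other places define who counts:

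- Section 5.9 repeats the replacement list without any preladenant exposure bullet. For the infusion it reads "They receive less than 90% of the total pembrolizumab infusion in Cycle 1", and the condition attached is "and did not experience a DLT".
- Section 8.5.1 takes for DLT evaluation "ASaT subjects that were observed for safety for 21 days after the first dose of assigned treatment", or those with an earlier DLT. It sets no exposure minimum.

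**The concern.** An under-dosed subject should fall into one of two groups: a DLT if drug toxicity caused the missed doses, or non-evaluable if it did not. Because the two AE conditions differ, a third group remains. It consists of subjects whose missed doses were not caused by toxicity but who happened to have some drug-related AE. They stay in the denominator as having tolerated a dose they did not fully take.

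The route into this group is open. After the witnessed Day 1 dose, preladenant is taken unsupervised at home (Section 5.2). Mild AEs are common: Section 4.1.3.1 reports insomnia in 24% of healthy volunteers on preladenant against 3% on placebo, and headache in 15% against 3%. In Arm 2, Section 7.2.4 assigns causality to the whole regimen by default, so a mild AE of either drug can block replacement.

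The DLT rate is the primary endpoint, and Section 5.2.1.2 allows escalation on 0 DLTs among three subjects. An error in this direction makes a dose look better tolerated than it is.

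**Working it through.** **Do the thresholds coincide?** Two doses a day for 21 days gives 42 planned doses. Receiving 31 is 31/42 = 73.8% (11 missed, 26.2%). Receiving 32 is 32/42 = 76.2% (10 missed, 23.8%). Both rules therefore start at 11 missed doses, and the mismatch lies only in the AE condition.

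**How each rule treats a subject with 11 or more missed doses**

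| Reason for missed doses | Any drug-related AE? | Criterion 9 | 5.2.2.1 preladenant bullet | Result |
|---|---|---|---|---|
| Drug-related AE | Yes | DLT | not replaced | DLT |
| Other | No | no | replaced | Non-evaluable |
| Other, not covered by another bullet | Yes, any grade | no | not replaced | Counts as DLT-free |

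**The plan's own grid.** I recomputed Table 4 from its footnote: target 0.30, Beta(1,1) prior, both epsilons 0.03. The posterior is Beta(1+x, 1+n−x), and the decision is the interval with the largest unit probability mass among (0, 0.27), (0.27, 0.33) and (0.33, 1). DU is set when P(p > 0.30) > 0.95; the 0.95 cutoff is my assumption, as the documents do not state one. All 78 cells in rows 0 to 6 match. Rows 7 and 8 are broken in the extracted text and were not scored.

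**Effect of one extra DLT-free subject, read from Table 4.** 2/3 D becomes 2/4 S; 3/4 DU becomes 3/5 D; 1/5 S becomes 1/6 E; 3/5 D becomes 3/6 S; 4/6 DU becomes 4/7 D; 2/10 S becomes 2/11 E. Every change is to a less cautious decision.

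**Effect if one such subject is among the first three.** Let p be the true DLT rate at full exposure and r·p the DLT risk of the under-dosed subject. The documents give no value for r, so I assume r = 0.5 to 0. Then P(0/3) is (1−p)³ if the subject is replaced by a fully exposed one and (1−p)²(1−r·p) if the subject is kept.

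| p | Replaced | Kept, r = 0.5 | Kept, r = 0 |
|---|---|---|---|
| 0.30 | 0.343 | 0.49 × 0.85 = 0.4165 | 0.490 |
| 0.40 | 0.216 | 0.36 × 0.80 = 0.288 | 0.360 |
| 0.50 | 0.125 | 0.25 × 0.75 = 0.1875 | 0.250 |

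**Average effect.** Let f be the chance that a subject falls in the gap. Assume 5-10% are under-dosed for reasons other than an AE, and 24-70% have some drug-related AE. The 24% borrows the insomnia figure in Section 4.1.3.1; the other values have no source in the documents. Then f runs from 0.05 × 0.24 = 1.2% to 0.10 × 0.70 = 7%. The chance of at least one such subject in three is 1−0.988³ = 3.6% to 1−0.93³ = 19.6%. Each subject is DLT-free with probability 1−p+f·p·(1−r). At p = 0.40:

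- r = 0, f = 1.2%: 0.6048³ = 22.1%
- r = 0, f = 7%: 0.628³ = 24.8%
- r = 0.5, f = 1.2%: 0.6024³ = 21.9%
- r = 0.5, f = 7%: 0.614³ = 23.1%

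Against 21.6%, the average increase is 0.3 to 3.2 percentage points.

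**The case against.** The case for treating this as minor has four parts.

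- **Scope.** A reader might infer that every unrelated reason for missing doses falls in the gap. It does not. The bullet on logistical issues and unrelated medical events already covers travel and arguably some disease symptoms. Sections 5.2.1.4 and 5.8.1 also list non-compliance as a reason to stop treatment, and a subject who leaves the trial before completing the safety evaluations is replaced. This stands and narrows the point. But 5.8.1 says that stopping treatment is not withdrawal from the trial, so a non-adherent subject who stays under observation is still counted.
- **Size.** A reader might take 21.6% to 36.0% as the effect on the design. That figure assumes that such a subject is present and has no DLT risk at all. Someone who took up to 31 of 42 doses and had a drug-related AE was plainly exposed. The 24% counts AEs reported by healthy volunteers, not drug-related AEs in this population, and the assumed frequencies are not reduced for reasons already covered by replacement. This stands; the averaged figures are the fair summary.
- **Attribution.** Under 8.5.1 an under-dosed subject observed for 21 days counts with or without an AE, so the AE phrase is not alone responsible for the SAP's DLT rate. This also stands. It means that editing 5.2.2.1 alone would not be enough.
- **Safeguards.** Capsule counts (7.1.1.9), preladenant sampling on Cycle 1 Days 8 and 15, and review of safety and any available PK before the next dose level opens (5.2.1.4) could reveal under-exposure. They are useful, but none removes the subject from Table 4, and 5.2.1.2 bases escalation decisions on DLT occurrence.

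**Conclusion.** The gap is real but narrow. It rests on the wording of 5.2.2 and 5.2.2.1, not on any assumed frequency. Followed exactly, the rules count as DLT-free a subject who missed 11 or more of 42 doses for a reason that no other replacement bullet covers, provided the subject had any drug-related AE. The clear case is non-adherence or unexplained missed home doses. Neither 5.9 nor 8.5.1 corrects this.

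The bias is toward under-counting DLTs. At a true 40% DLT rate it matters when it happens (0/3 at 28.8-36.0% instead of 21.6%, for assumed DLT risk of half to none) but is small on average (about 22-25%, for an assumed 1-7% frequency). The documents do not support a claim that escalation is seriously distorted overall. The change is worth making because the error favours escalation in the primary endpoint and costs little to remove.

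**What to change.** In the preladenant bullet of 5.2.2.1, replace the condition that the subject had no drug-related AE with the one 5.9 already uses for the infusion, "and did not experience a DLT". A subject with 75% or less of the Cycle 1 doses is then either a DLT or replaced. AE-driven missed doses remain DLTs under criterion 9, and treatment-related discontinuation in Cycle 1 remains a DLT under criterion 8.

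Two further edits are needed for this to take effect:

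- Align the pembrolizumab bullet of 5.2.2.1, which refers to any drug-related event, with 5.9, which refers to a DLT.
- Put one DLT-evaluable definition, including the preladenant exposure minimum, into both 5.9 and 8.5.1, so that the dose decisions and the reported DLT rate use the same subjects.

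The cost is a short wording amendment and an occasional replacement subject in Part 1. On the assumed frequencies, the approximately 52 planned Part 1 subjects would include 52 × 0.012 = 0.6 to 52 × 0.07 = 3.6 such cases, probably toward the low end. The replacement process already exists.

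### Sections 5.2.2.1, 5.9 and 8.5.1 conflict on whether a subject with an observed Cycle 1 DLT still counts after a later, unrelated replacement event, and none says which count enters Table 4

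*Combined protocol and SAP*

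**What the plan says.** Three sections of the combined protocol and SAP define who counts for DLT purposes.

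**Section 5.2.2.1** lists six grounds on which a subject is non-evaluable and is replaced. It then states: "Non-evaluable subjects will not be counted toward the cohort total for DLT evaluation". The grounds differ in how they treat a subject who has already had toxicity:

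- The pembrolizumab under-dosing rule exempts such a subject: "because the infusion had to be discontinued due to an infusion reaction) and did not experience a drug-related event".
- So does the preladenant under-dosing rule: "of preladenant doses intended for the trial during Cycle 1 and did not experience a drug-related AE".
- Leaving the trial looks only at the reason for leaving: "They discontinue from the trial prior to completing all safety evaluations due to reasons other than drug-related AEs".
- Prohibited medication looks only at what the drug is for: "They must take a prohibited concomitant medication during Cycle 1, unless this medication is used to treat a study drug-related AE".
- Unrelated procedures or logistics have no exemption: "They must undergo medical / surgical procedures or have logistical issues not related to study therapy".
- The sixth ground, enrolled but never treated, needs none.

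**Section 5.9** has a shorter list of three grounds. Its infusion rule exempts subjects who had a DLT, which differs from the drug-related event named in 5.2.2.1. Its rule on leaving the trial again has no exemption: "They discontinue from the trial prior to completing all the safety evaluations for reasons other than treatment-related adverse events". It has no prohibited-medication, procedure or preladenant under-dosing rule.

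**Section 8.5.1** defines the set for DLT evaluation as treated subjects who were observed for 21 days or who "experienced a DLT prior to 21 days after the first dose of assigned treatment will be used". It adds that replacement subjects are evaluable on the same terms, and it does not exclude a subject who was replaced.

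**The concern.** Sections 5.2.2.1 and 8.5.1 both speak of DLT evaluation but answer one question differently: does an observed DLT still count if the same subject later, within Cycle 1, starts an unrelated prohibited drug, has an unrelated procedure or withdraws for an unrelated reason? Read literally, 5.2.2.1 says no and 8.5.1 says yes.

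This matters because Table 4 is a small-number grid in which one subject often changes the decision. Escalation, the unacceptably-toxic label and the room left to enrol at a dose all come from it. If the sites and the sponsor apply 5.2.2.1 during the trial and the statistician applies 8.5.1 at the end, a dose decision could rest on one count while the DLT rate at that dose is reported on another.

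**Working it through.** **1. Reproduce Table 4.** Inputs from Table 4: target 0.30, prior Beta(1,1), epsilon 0.03 on each side. With x DLTs in n subjects the posterior is Beta(1+x, 1+n−x). The decision is the interval with the largest posterior probability per unit length among (0, 0.27), (0.27, 0.33) and (0.33, 1), which give E, S and D. DU is assigned when the decision is D and P(p > 0.30) > 0.95; the 0.95 is an assumption, since the documents give no cut-off. All 78 filled cells in rows 0 to 6 match.

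Two cells by hand:

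- 0/3, Beta(1,4), CDF 1−(1−u)^4. E: 0.716/0.27 = 2.65. S: (0.798−0.716)/0.06 = 1.37. D: 0.202/0.67 = 0.30. Escalate.
- 1/4, Beta(2,4), CDF 10u²−20u³+15u⁴−4u⁵. E: 0.409/0.27 = 1.52. S: (0.532−0.409)/0.06 = 2.05. D: 0.468/0.67 = 0.70. Stay.

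**2. Apply both definitions.** Suppose one DLT subject meets one of the three unprotected rules and is replaced by a subject without a DLT. Under 5.2.2.1 the DLT subject leaves and the replacement enters: (x−1)/n. Under 8.5.1 the DLT subject stays and the replacement is added: x/(n+1).

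| Observed | 5.2.2.1 read literally | 8.5.1 |
|---|---|---|
| 1/3 Stay | 0/3 Escalate | 1/4 Stay |
| 2/3 De-escalate | 1/3 Stay | 2/4 Stay |
| 3/3 DU | 2/3 De-escalate | 3/4 DU |
| 2/6 Stay | 1/6 Escalate | 2/7 Stay |
| 4/6 DU | 3/6 Stay | 4/7 De-escalate |

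The definitions give different decisions in four of these five rows and the same one in the 2/3 row. No assumption about frequency is needed, only that the replacement has no DLT.

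**3. Can the case arise?** Yes, because 5.8.1 separates stopping treatment from withdrawing from the trial. A subject taken off drug for a DLT therefore remains in the trial, and a later event can meet a replacement rule. Suppose a DLT on Day 8, treatment stopped, and fentanyl started for cancer pain on Day 15. Table 11 lists fentanyl, and 5.5.2.1 extends its restrictions to two weeks after the treatment period; the gap here is 15 − 8 = 7 days. An unrelated procedure or an unrelated withdrawal of consent in the rest of Cycle 1 would also qualify.

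**4. Is there a systematic bias?** Let p be the true DLT rate and q the chance of meeting one of the three rules, equal with and without a DLT. The counted rate under 5.2.2.1 is p(1−q)/[p(1−q)+(1−p)(1−q)] = p. Individual DLTs are discarded, but the expected rate does not move. A downward bias needs DLT subjects to meet the rules more often than others, and the documents give no figure for that.

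**The case against.** The strongest reply is that 8.5.1 already settles the matter. It keeps the DLT subject and has no exclusion for replaced subjects. Section 5.2.1.2 ties dose decisions to DLTs occurring at a dose, and Table 4 is labelled by subjects treated and subjects with a DLT. Section 5.2.2 attaches no evaluability condition to a DLT. Dose decisions are made jointly by investigators and sponsor, who would see the event.

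Much of this stands. A reader might infer from 5.2.2.1 alone that the plan deletes observed DLTs, biases the primary endpoint and pushes the recommended dose upward. The documents do not support that. The DLT analysis set is the one in 8.5.1, which retains these subjects, and step 4 shows no expected bias without an unsupported difference in trigger rates.

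The cases are also narrow. A drug given to treat the DLT is exempt under the prohibited-medication rule. Stopping treatment because of the DLT does not meet the rule on leaving the trial. Proton-pump inhibitors are not a sound example: 5.5.2.1 ends that restriction 5 days after the last preladenant dose. Even the fentanyl case has some friction, because 5.5.2.2 says no therapy is prohibited in post-treatment follow-up. The procedure and withdrawal cases do not depend on any of this.

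What does not stand is that 8.5.1 governs cohort decisions. It sits among the analysis populations, while 5.2.2.1 and 5.9 are the operative rules on replacement and cohort totals. No section ranks them.

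**Conclusion.** The point holds as a contradiction between sections. Three replacement rules in 5.2.2.1, and one in 5.9, have no exemption for an observed DLT; 8.5.1 retains it; and the count that enters Table 4 is not identified. The size is one subject in the count. That is enough to separate Escalate from Stay (one DLT in three, or two in six) or Stay from De-escalate (four in six), given a DLT-free replacement. How often this would happen cannot be estimated from the documents. It should be corrected because the grid drives every escalation step and the correction is small. It is not evidence that the planned DLT-rate analysis is wrong.

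**What to change.** Reconcile the three sections. Before the lists in 5.2.2.1 and 5.9, state that a subject with a DLT in Cycle 1 is always evaluable, is counted as a DLT in Table 4 and is not replaced, and that the replacement criteria apply only to subjects without a DLT. This carries the protection already implied by 8.5.1 into the escalation count. With no replacement the observed cells stand: 1/3 remains Stay and 4/6 remains DU.

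The cost is one sentence in two sections, with no added procedures. The statistical downside is a slightly conservative count, because DLT subjects are always kept while some DLT-free subjects are replaced. The counted rate is p/[p+(1−p)(1−q0)], where q0 is the share of DLT-free subjects replaced. With p = 0.30 and an assumed q0 of 0.10 this is 0.30/(0.30+0.70×0.90) = 0.30/0.93, or about 32%.
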